8.4.1 Safety Events of Special Interest

A safety event of special interest (SESI) is a select safety event that could be related to the study intervention. Safety ESIs will be solicited for their occurrence (No or Yes) and assessed by the investigator/delegate (defined as a clinician licensed to make a diagnosis) for intensity, causality, and association to provide uniform data collection of all events.

Safety ESIs are expected, pre-specified events, so they will not be reported in an expedited manner to the FDA but will be reviewed by the MM and the Data Safety Monitoring Board (DSMB) convened by NICHD and reported to the FDA in the annual report.

The only SESI for this study will be the QTc interval obtained by ECG prior to study drug administration, 30 hours after study drug administration, and at the final study visit (96 hours post-administration).

8.5 Collection Period and Reporting Procedures

Adverse Event information will be gained from direct monitoring of the study participants as well as from clinician observation and self-reporting by the study participants. The investigator/delegate (defined as a clinician licensed to make a diagnosis) must document his or her assessment of severity and causality in the participant records in a timely manner and submit safety reports as required by his or her IRB.

Death irrespective of causality, identified as either an unsolicited or solicited event (i.e., SESI), at any time through end of study will be reported.

Serious Adverse Events/SUSARs will be collected for all participants, following the execution of informed consent through 7 days post last sample collection, and reported on the AE/SAE electronic case report form (eCRF).

Safety ESIs (Section **4.6.1** and **8.4.1**) will be collected for all participants following the execution of informed consent through 7 days post last sample collection, and assessed for intensity, causality, and association, and reported in the data system. To determine if SESIs are dose related, additional data around solicited safety events will be recorded.

Adverse Events will be recorded from the time of methadone administration until 96 hours (the final study visit) and reported in the data system.

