3 OBJECTIVES AND OUTCOME MEASURES

	Objective	Measures	Endpoints
Primary	Characterize the PK of methadone hydrochloride injection	Plasma concentrations	1. Clearance (CL) 2. Volume of distribution (Vz) 3. Half-life (t _{1/2}) 4. Area under the curve (AUC) 5. Maximum concentration (C _{max}) 6. Time to maximum concentration (T _{max}) 7. Minimum concentration (C _{min}) 8. Elimination rate constant (k _e)
Secondary	Characterize the PD effect of methadone hydrochloride injection	1. Dark-adapted pupillometry 2. Observed sedation 3. Thermal pain tolerance thresholds 4. Subjective self-assessment of methadone effects using visual analog scale (VAS)	Change in pupillometry, observed sedation, thermal pain tolerance thresholds, and VAS from pre-dose to each post-dose time point
Secondary	Characterize the tolerability of methadone hydrochloride injection	1. Adverse events (AEs) 2. Serious adverse events (SAEs) 3. Suspected Unexpected Serious Adverse Reactions (SUSARs) 4. Safety events of special interest (QTc)	For AEs, SAEs, SUSARs: Proportion of participants from baseline to the end of safety follow-up For SESI: Change in QTc from baseline to the end of safety follow-up
Exploratory	Characterize exposure-response relationships	Plasma concentrations and VAS	Correlation of plasma concentrations to VAS score at each post-dose VAS time point

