4.3 Duration of Participant Participation

The screening visit will occur 0-30 days prior to study start. From time of consent, participation may be up to 96 ± 8 hours after study drug administration, wherein the first 30 hours is an inpatient visit, including study drug administration and PK blood draws, followed by a 48 hour, and 72-hour follow-up. The final visit will occur at 96 hours.

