6.2 Screening/Enrollment (Day -30 to 0)

The investigator will screen participants according to the eligibility criteria (Section 5.2). Screening must remain impartial (no selectivity) to prevent bias.

Potential candidates' eligibility must be confirmed, or re-confirmed, and documented in the source records by the Study PI (or designee), prior to the conduct of any study procedures. Potential candidates will be educated on the study procedures, benefits, and potential risks as part of the applicable informed consent. Following consent, the enrolled participant's demographic information will be recorded, and the participant will undergo the following:

- Physical examination, including capturing weight and height
- Vital signs (heart rate, blood pressure, respiratory rate and oxygen saturation)
- Medical history
- ECG to determine QTc
- Review of concomitant medications
- Blood collection for clinical laboratory assessments (Section 6.7.2)
- Serum quantitative pregnancy test
- Urine drug screen to test for illegal and prescription drugs
 - Methamphetamine
 - Morphine-a drug in the opiate class
 - Marijuana
 - Amphetamine
 - Barbiturates
 - Benzodiazepines
 - Cocaine
 - Phencyclidine
 - Methadone
 - Ecstasy/MDMA
- Breathalyzer

For alcohol and substance abuse, the study team will query the potential participant about past and current drug and alcohol use or treatment of use, then document said testimony, which will be validated by the urine drug screen and breathalyzer.

This visit will occur up to 30 days before the inpatient visit to allow adequate time for the return of clinical laboratory results.

Refer to MOP for details.

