6.5 Final Study Visit (96 hours post-drug administration)

At approximately 96 ± 8 hours after methadone administration, the final study visit will be in-person at the DEPRU and include the following:

- Review of concomitant medications
- Blood collection for PK analysis
- Electrocardiogram for QTc
- Pupillometry, goggles for dark-adapted pupil diameter
- Vital signs, including RR, end-expired CO₂, HR, BP, and SpO₂
- Observed sedation, MOAA/S
- Thermal pain tolerance threshold
- Subjective self-assessment, VAS
- Safety event assessment

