8 ASSESSMENT OF SAFETY

8.1 Specification of Safety Parameters

Studies performed under IND FDA regulations require reporting based on the definition included in 21 CFR 312.32 (a), regardless of the definition of AE used in the protocol.

An **adverse event (AE)** is any untoward medical occurrence in humans, whether or not considered intervention-related, which occurs during the conduct of a clinical trial. (Any change in clinical status, ECGs, routine labs, x-rays, physical examinations, etc., that is considered clinically significant by the Study PI is considered an AE).

An **unexpected adverse event** is any AE, of which the nature, specificity, or severity is not consistent with the applicable product information (e.g., package insert/approved label) or investigational plan.

A **suspected adverse reaction (SAR)** is any AE for which there is a reasonable possibility that the intervention caused the AE. A reasonable possibility implies that there is evidence that the intervention caused the event.

An **adverse reaction (AR)** is any AE caused by the intervention.

A **serious, unexpected, suspected adverse reaction (SUSAR)** is a SAR that is both serious and unexpected.

All AEs related to methadone administration will be reported. Safety will be assessed by frequency and incidence of reported AEs, SAEs, and SUSARs. A safety Data Monitoring Safety Monitoring Board (DSMB) convened by NICHD will review data and safety information from study participants.

All AEs related to the study procedures or assessments (e.g., blood draws) and SUSARs related to study product will be reported. Safety ESIs will be recorded.

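### Adverse-event recording starts too late to capture the procedure-related events the protocol analyses, and the QTc and safety-endpoint windows have no usable end

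*Combined protocol and SAP*

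**What the plan says.** All references are to the protocol; its section 11.3 leaves further detail to a statistical analysis plan.

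- **AE recording (section 8.5):** "Adverse Events will be recorded from the time of methadone administration until 96 hours (the final study visit".
- **SAEs, SUSARs and the safety event of special interest (section 8.5):** collected "following the execution of informed consent through 7 days post last sample collection".
- **What must be reported (section 8.1):** "All AEs related to the study procedures or assessments (e.g., blood draws" are to be reported. Section 11.3.2 places procedure-related AEs first in its list of safety incidences.
- **The event of special interest (sections 4.6.1 and 8.4.1):** QTc only, from ECGs before dosing, at 30 hours and at the 96-hour visit.
- **Last visit (sections 4.3 and 6.5):** "The final visit will occur at 96 hours"; "At approximately 96 ± 8 hours after methadone administration, the final study visit will be in-person at the DEPRU". The last PK sample in Table 4 falls at the same time. Table 3 lists nothing later, and its safety-events row has no mark at screening.
- **Endpoints (sections 3 and 11.1.2):** AEs, SAEs and SUSARs are given one interval from baseline to the close of safety follow-up. QTc has the same interval: "Change in QTc from baseline to the end of safety follow-up". Neither end is defined.
- **Completion (section 4.9.1):** safety follow-up runs to the last visit, with no further seven days.

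**The concern.** An incidence needs a collection rule that covers the events it counts. Here one section asks for procedure-related AEs, another analyses them, and the section that governs collection starts the clock after several study procedures are over. Site staff following section 8.5 and staff following section 8.1 would enter different events, and the reported incidence would depend on which section they read.

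The QTc window has the opposite fault: it extends beyond any planned measurement. Because the end of safety follow-up is undefined, an analyst could take it as 96 hours (section 4.9.1) or about Day 11 (section 8.5). The first is supported by data for AEs, SAEs and QTc alike. The second is supported only for SAEs that happen to be reported. At stake are the definition and denominator period of the secondary tolerability results.

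**Working it through.** **1. The plan's own duration.** Section 6.2: "This visit will occur up to 30 days before the inpatient visit". Section 4.3: "participation may be up to 96 ± 8 hours after study drug administration". So 30 + 96/24 = 34 days, which reproduces the synopsis figure.

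**2. Where the section 8.5 windows end.**
- AEs: 0 to 96 h, that is 4 days.
- SAEs, SUSARs and QTc: last sample + 7 × 24 h = 96 + 168 = 264 h, or Day 11.0. With the ± 8 h visit window: 88 + 168 = 256 h (Day 10.7) to 104 + 168 = 272 h (Day 11.3).
- Share of the post-dose QTc window with no planned ECG: 168/264 = 64% (168/272 = 62% to 168/256 = 66%).
- A final visit at the late edge falls at 104 h, so a fixed 96-hour AE cut-off can close up to 8 h before that visit.

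**3. What happens before AE recording opens.**
- Screening (sections 6.2 and 6.7.2): blood draw and ECG.
- Day 0 (sections 2.4.3, 6.3, 6.8.5 and 7.3; Tables 4 and 5): IV access, pre-dose ECG, PK sample 1, the baseline heat test (three stimuli) and ondansetron 15 minutes before methadone.

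The protocol itself names harms from these: burns, electrode skin irritation and ondansetron headache (section 2.4), bruising (section 2.4.1) and phlebitis (section 2.4.3).

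**4. How much Day 0 exposure this is.** One of 18 PK draws (6%) and one of 15 heat-test time points (7%) come before dosing. All screening procedures do. The documents give no event rates, so the number of events lost cannot be computed.

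**5. Serious against non-serious.** SAE collection begins at consent, so serious pre-dose events are covered. The gap concerns non-serious events only.

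**6. Section 8.6 against section 8.5.** Section 8.6 asks for follow-up of procedure-related AEs that are ongoing at the last dose. In a single-dose study such an event began no later than dosing, so section 8.6 presupposes pre-dose recording that section 8.5 does not provide.

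**7. The undefined baseline.** For SAEs it could mean consent and for AEs the methadone dose. For QTc it could be the screening ECG (up to 30 days earlier) or the Day 0 pre-dose ECG. One word cannot serve all of these without a definition.

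**The case against.** The strongest defence is that different windows for AEs and SAEs are common, and that passive SAE reporting after the last visit is an acceptable design. Both points stand. Section 8.5 names participant self-report as a source, section 8.6 starts the reporting clock at site awareness, and related events are followed to resolution. A manual of procedures and a safety monitoring plan exist that were not available here.

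Sections 8.1 and 8.6 can also be read as bringing procedure-related AEs in regardless of section 8.5. That makes loss of these events a consequence of one reading rather than a certainty, but it confirms that the sections conflict. Bruising or phlebitis still present after dosing might be recorded anyway.

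Four stronger inferences are tempting, and the documents do not support them:

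- **That no one would hear of events after 96 hours.** The text shows only that no later contact is scheduled.
- **That 34 days is wrong because 30 + 4 + 7 = 41.** The 34 days correctly describe the visits; a passive reporting tail need not count as participation.
- **That slow elimination makes late events likely.** Section 2.1.1 gives a half-life of 8 to 59 h. The fraction left at 96 h, by simple exponential decline, runs from 2^(-96/8) = 0.02% to 2^(-96/59) = 32%. That range settles nothing and is not an event rate.
- **That methadone's tolerability is made to look better.** An event before the methadone push cannot be caused by methadone, and the planned QTc-change data are complete at 96 hours.

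**Conclusion.** The point holds as a conflict between collection rules and reported quantities. Read literally, section 8.5 omits non-serious AEs from pre-dose study procedures that sections 8.1 and 11.3.2 require. It also runs the QTc window 168 hours past the last planned ECG, and the endpoint definitions in sections 3 and 11.1.2 leave both ends open.

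The practical size is modest. On Day 0 the uncovered share is about 6% to 7% of PK draws and heat-test time points, plus all screening procedures. The direction and amount of any change in the reported incidence are unknown. Only the secondary tolerability results are affected; the primary PK analysis and the sample size are not.

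This rests on two assumptions: that section 8.5 governs data entry, and that no unseen operating document already widens the AE window. Whether an event from the pre-dose ondansetron counts as procedure-related is not stated and needs a decision.

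**What to change.** 1. **Section 8.5 and Table 3.** Record AEs related to study procedures from the first study procedure after consent; at the very least from the first Day 0 procedure, though that still misses the screening draw and ECG. Mark the matching column in the safety-events row. State how ondansetron events are classed. Close AE recording at the final visit itself rather than at a fixed 96 hours.
2. **Section 11.3.2.** Tabulate pre-dose events separately from treatment-emergent AEs. List any in screen failures, because the section 11.2 safety population includes only dosed participants.
3. **Sections 8.5, 3 and 11.1.2.** End the QTc event window and the QTc endpoint at the 96-hour ECG (or at the last ECG obtained, after early withdrawal), and name the baseline ECG. A telephone call could not supply a QTc value.
4. **Sections 3 and 11.1.2.** State the AE, SAE/SUSAR and QTc windows separately, each with a defined start and end. If the seven-day SAE tail is kept, report SAEs after the 96-hour visit as spontaneously reported unless a contact is scheduled.

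The cost is an amendment of wording and a few more AE entries among about 20 participants. No visit, sample or analysis method changes.

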8.6 Safety Event Follow-up and Sponsor Reporting

Adverse Events, SAEs, and SESIs **directly related** to study intervention/procedures will be followed until resolution, even if this period extends beyond the study-reporting period.

Resolution of an AE is defined as the return to pretreatment status or stabilization of the condition with the expectation that resolution will remain chronic. If the event resolves during the study or follow-up period, a resolution date should be documented in the data system.

Adverse Events **directly related** to study intervention/procedures and SESIs (without a causal relationship to study intervention, that are not defined as an SAE) will be reported in the data system within 7 days of identification/site awareness.

Adverse Events considered related to study intervention/procedures and all SAEs/SESIs ongoing at the time of the last dose of study intervention will be followed for as long as necessary to adequately evaluate the participant's safety or until the event stabilizes. If the event resolves during the study or follow-up period, a resolution date should be documented in the data system.

Serious Adverse Events, SUSARs, and SESIs that are associated with any of the criteria that define the event as an SAE will be reported in the data system within 24 hours of identification/site awareness. Upon entry in the Electronic Data Capture (EDC) system, these events will generate an automatic email notification to the MM and the sponsor. The investigator/delegate (defined as a clinician licensed to make a diagnosis) must document his or her assessment of intensity, causality, and association in the participant records in a timely manner and submit safety reports as required by his or her IRB.

The MM will review all safety events at the time they are reported. Any event that requires expedited reporting based on federal regulations (21 CFR 312.32) will be forwarded to the IND sponsor. The IND sponsor or its representative will submit expedited safety reports (e.g., IND safety reports) to the regulatory agencies, as necessary.

8.6.1 Discontinuation of a Participant Due to Adverse Events

Any participant who experiences an AE may be withdrawn at any time from the study at the discretion of the investigator. The AE(s) should be reported in the EDC system, and the participant's progress should be followed until the AE is resolved or considered stable. The MM must be notified. If the AE may be related to overdose of study treatment, the package insert should be consulted for details of any specific actions to be taken.

8.7 Pregnancy

Although not considered an AE, pregnancy must be reported on the specific pregnancy report form. If a participant is found to be pregnant during the study, the site must immediately report it. The site must document that they contacted the participant, advised the participant to obtain appropriate prenatal medical care, and referred the participant for such care. In addition, per the consent, researchers will follow the participant for the duration of the pregnancy and to obtain information (via direct examination or medical record review) to determine whether the resulting fetus/baby survived delivery or had any congenital abnormalities. If the fetus/newborn does not survive delivery or any congenital abnormalities are present, these must be reported as an SAE following the usual requirements for SAE reporting. Please note that if a pregnancy is reported, the participant's subsequent weight, vital sign, and laboratory data will not be included in analyses for these variables. If the pregnancy is terminated early within the first 12 weeks of the pregnancy, inclusion of the participant's subsequent weight/height, vital signs, and laboratory data in the analyses will be determined by the PTN study team.

8.8 Regulatory Reporting

Any event that requires expedited reporting based on federal regulations will be forwarded to the IND sponsor via reporting on the study specific eCRF. The IND sponsor or its representative as detailed in the Transfer of Regulatory Obligations will submit expedited safety reports (e.g., IND safety reports) to the FDA and other regulatory agencies as necessary and will inform the investigators of such regulatory reports. Site investigators must submit safety reports as required by their IRB. Documentation of the submission and receipt by the IRB must be retained for each expedited safety report.

Any event that requires reporting to Regulatory Authorities (e.g., SUSARS) based on applicable national regulations will be forwarded to the IND sponsor in time to meet reporting requirements.

8.9 Data and Safety Oversight (Medical Monitor/Data Safety Monitoring Board)

The study will be monitored by the BPCA Data Safety Monitoring Board (DSMB). The NIH charters the DSMB to support all research activities conducted under the BPCA PTN.

In addition, the study has designated a qualified and experienced physician not otherwise associated with this protocol to serve as the Medical Monitor (MM) and review all safety events at the time they are reported and/or updated. The MM may request additional information regarding a site reported SAE; the Study PI is expected to provide requested information or materials to the MM in an expeditious manner to support the writing/submission of study safety reports. The MM will be available to study sites as needed. The study IND sponsor will also review all SAEs to determine regulatory reporting and will be available to sites as needed.

If safety concerns are identified, the MM may request a meeting of the DSMB to review safety data. The MM will also provide an initial report to the PTN PI/IND sponsor and an unbiased written report to the DSMB of the event per the DSMB charter/safety monitoring plan. At a minimum, the MM will comment on the outcomes of the safety event and the relationship of the safety event to the study product/intervention. The MM will also indicate whether they concur with the details of the report provided by the study site investigator. If no safety events prompt review at an earlier time point, the DSMB will review safety events per the DSMB charter.

The DSMB will convene and make recommendations on termination of the study based on review of safety reports and halting rules. The safety data will be compiled by the TDS. Based on the recommendations of the DSMB, PTN, and NIH/NICHD, the IND sponsor will decide to terminate or continue the study.

Ad Hoc Meetings of the DSMB: The DSMB may convene an ad hoc meeting to discuss any issue of data and safety raised by the site investigator, MM, the IND sponsor, NICHD, or a member of the DSMB. At the discretion of the investigators, the IND sponsor, NICHD, and DSMB members, a non-serious safety event that is associated with the product or procedures may be considered as a trigger for an ad hoc DSMB meeting to assess the safety of the product/intervention, without resulting in halting the enrollment of the trial.

9 STUDY TERMINATION / HALTING

9.1 Study or Site Halting Criteria / Termination Criteria

This study may be terminated at any time by NICHD, the IND sponsor, or the DSMB. Reasons for termination include, but are not limited to, if in their judgment, no further benefits are to be achieved from the study or the intervention presents an unreasonable and significant risk to participants. If the study is terminated, notifications will be made to the regulatory authorities (e.g., FDA), investigators, IRBs, and study participants, in accordance with all applicable regulations governing the study and site/investigator.

